3.3 Protocol Map

3.4 Study Outcomes

The primary outcome will be histologic response, defined as a post-treatment esophageal eosinophil count of <15 eos/hpf.⁴¹ The esophageal eosinophil counts will be quantified using our previously validated protocol.⁴²

The secondary outcomes will be: 1) change in the absolute esophageal eosinophil count; 2) improvement in the endoscopic appearance, as measured by a validated endoscopy score,⁴³ and 3) improvement in symptoms, as measured by a validated dysphagia symptom score.⁴⁴

4 Subject Selection and Withdrawal

4.1 Inclusion Criteria

- 1) Age 16-80 years old
- 2) Meet one of the following:
 - a. Active EoE as per consensus guidelines OR
 - b. Undergoing upper endoscopy for a clinical suspicion of EoE
- 3) No prior history of dietary elimination therapy

4.2 Exclusion Criteria

- 1) Concomitant eosinophilic gastroenteritis
- 2) Any corticosteroid exposure in the 4 weeks prior to their baseline endoscopic exam
- 3) Previous esophageal surgery
- 4) Medical instability that precludes safely performing upper endoscopy
- 5) Inability to read or understand English
- 6) Pregnant women

4.3 Subject Recruitment and Screening

Patients with active or suspected EoE or who are undergoing or recently underwent routine care upper endoscopy will be screened by research personnel. These patients will be identified by screening the endoscopy and CEDAS clinic schedules or via referrals from other physicians. Once a potential subject is identified, study personnel will contact the potential subject to describe the study and gauge interest in participating. Initial contact may be in person or on the phone. If the patient is interested in participating, then the study coordinator or other study staff will obtain written informed consent from the subject.

4.4 Early Withdrawal of Subjects

4.4.1 When and How to Withdraw Subjects

Subjects have the right to withdraw from the study at any time, for any reason, and without repercussion. The investigator, [name], has the right to withdraw a patient from the study in the event of an intercurrent illness, adverse event (AE), treatment failure, protocol violation, and for administrative or other reasons. An excessive rate of withdrawals would reduce the amount of data available for analysis and limit the ability to interpret the study results; therefore, unnecessary withdrawal of patients should be avoided.

If subjects become pregnant during the study, then their participation will be stopped.

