After completion of the EGD and/or collection of EGD records and previous biopsies if an EGD was previously completed), and confirmation of eligibility, subjects will be scheduled for a routine care nutrition counseling appointment. Two weeks prior to the routine care nutrition counseling appointment, subjects will begin the dysphagia symptom questionnaire (DSQ). During the routine care nutrition counseling appointment, the subject will receive counseling on which foods to eliminate based on the T-cell and IgG4 results from the research biopsies. Subjects will also receive an allergy skin test during this visit. Results from the allergy skin test will not be used to drive food elimination diet.

Subjects will follow their assigned food elimination diet for 6 weeks. At 6 weeks subjects will be scheduled for a routine care esophagogastroduodenoscopy (EGD) with biopsies for clinical purposes. Two weeks prior to the 6 week EGD subjects will restart the DSQ. Data will be collected from the 6 week EGD but no research specific biopsies will be obtained during that visit. Research specific blood will be taken at this visit. Study participation is complete after completion of the 6 week EGD.

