6.2 Statistical Methods

To determine the response rate for the primary outcome, the number of subjects with <15 eos/hpf on follow-up endoscopy will be calculated. For secondary outcomes, median eosinophil counts, endoscopy scores, and symptoms scores will be compared before and after treatment with Wilcoxon signed-rank. These will be contextualized by calculating odds ratios and 95% confidence intervals where appropriate, so as not to

over-rely on p values alone. Patients who drop out or who have incomplete data for the outcomes will be excluded from analysis. Because this study's outcomes are determined after the treatment period and follow-up endoscopy, a subject must complete this end of treatment evaluation for us to be able to include their data in the analysis. We do not feel that selection bias would impact the analysis if there are incomplete data due to drop out. We are not performing a comparative analysis between groups, so drop out would not be dependent on different treatments administered in different study arms. In addition, in our experience with previous clinical studies of EoE, dropout rates have been quite low.

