6.3 Subject Population(s) for Analysis

Patients who drop out or who have incomplete data for the outcomes will be excluded from analysis

7 Safety and Adverse Events

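### Subjects withdrawn for an undefined treatment failure can leave the response-rate denominator before the week-6 biopsy

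*Combined protocol and SAP*

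**What the plan says.** Four parts of the plan have to be read together.

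- **Withdrawal (4.4.1).** The investigator "has the right to withdraw a patient from the study in the event of an intercurrent illness, adverse event (AE), treatment failure, protocol violation"; the list then extends to administrative and unspecified grounds. Neither this section nor any other defines treatment failure or says when it may be declared. The section adds that "unnecessary withdrawal of patients should be avoided", because losing subjects reduces the data available.
- **Follow-up after withdrawal (4.4.3).** Subjects who withdraw early may be asked to complete an end-of-study visit. It is not required.
- **Outcome (3.4, 3.1).** The primary outcome is "histologic response, defined as a post-treatment esophageal eosinophil count of <15 eos/hpf". The only endoscopy on the diet is the 6-week one, and "Study participation is complete after completion of the 6 week EGD".
- **Analysis (6.2, 6.3).** For the response rate, "the number of subjects with <15 eos/hpf on follow-up endoscopy will be calculated". Section 6.2 requires that "a subject must complete this end of treatment evaluation for us to be able to include their data in the analysis", and Section 6.3 repeats that "Patients who drop out or who have incomplete data for the outcomes will be excluded from analysis". No rule counts a withdrawn subject as a non-responder. Section 6.2 sets selection bias aside because there are no arms to compare and past dropout has been low.

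**The concern.** The trial estimates one proportion, with no control group. Its hypothesis is a response in at least 75% of patients (Section 2), and the observed rate is meant to inform a planned randomised study against empiric elimination (6.1). The denominator therefore carries as much weight as the numerator.

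Section 4.4.1 supplies a ground for leaving the study that is related to how the diet is working. Sections 6.2 and 6.3 then turn leaving into not being counted. The decision belongs to the investigator, who under Section 3.2 is also the sponsor. This differs from ordinary dropout, which the plan discusses: past experience of low dropout says nothing about removals started by the investigator. The absence of a comparison between arms does not help either. A single-arm proportion is biased whenever leaving the study is associated with the outcome.

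The enrolment plan makes such losses hard to see. Up to 30 subjects are enrolled to obtain 20 completers (6.1), so withdrawn subjects can be replaced and the target of 20 still met.

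**Working it through.** **1. The plan's own figure.** Section 6.1 gives 15 responders among 20 completers: 15/20 = 75.0%, which reproduces. Its 95% interval of 47–92% does not. The exact (Clopper-Pearson) interval for 15/20 is 50.9–91.3%, and the Wilson interval is 53.1–88.8%. That is a separate matter; exact intervals are used below.

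**2. Inputs that the documents do not give.** The number *w* withdrawn for treatment failure is assumed to be 0, 2 or 4. The true response rate *p* and the share *q* of non-responders withdrawn, used in step 5, are also assumed.

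**3. Effect on the reported rate if all *w* are true non-responders.** Reported rate = 15/20. Rate with them counted = 15/(20 + *w*).

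| *w* | Reported | With withdrawn counted | Exact 95% CI |
|---|---|---|---|
| 0 | 75.0% | 15/20 = 75.0% | 50.9–91.3% |
| 2 | 75.0% | 15/22 = 68.2% | 45.1–86.1% |
| 4 | 75.0% | 15/24 = 62.5% | 40.6–81.2% |

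**4. If some of the withdrawn would have responded.** With *k* responders among the *w*, the rate is (15 + *k*)/(20 + *w*).

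- *w* = 2: *k* = 0, 1, 2 gives 15/22 = 68.2%, 16/22 = 72.7%, 17/22 = 77.3%.
- *w* = 4: *k* = 0, 1, 2, 3, 4 gives 15/24 = 62.5%, 16/24 = 66.7%, 17/24 = 70.8%, 18/24 = 75.0%, 19/24 = 79.2%.

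The reported 75% is too high whenever the withdrawn would have responded at a rate below 75%. That is the expected direction for subjects judged to be failing, but it is not guaranteed.

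**5. Expected bias under selective withdrawal.** If a share *q* of non-responders is withdrawn and no responders are, the expected observed rate is *p* / (*p* + (1 − *p*)(1 − *q*)). The chance of 15 or more responders among 20 completers is the binomial tail at that rate.

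| *p* | *q* | Expected observed rate | Chance of ≥15/20 |
|---|---|---|---|
| 60% | 0 | 60.0% | 12.6% |
| 60% | 20% | 0.60/(0.60 + 0.40 × 0.80) = 65.2% | 25.2% |
| 60% | 33% | 69.2% | 38.7% |
| 60% | 50% | 0.60/(0.60 + 0.40 × 0.50) = 75.0% | 61.7% |

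At an assumed true rate of 60%, withdrawing half of the non-responders would produce the hypothesised 75% on average.

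**The case against.** The strongest reply is that early treatment failure is not the primary outcome. Histology is unknown until the week-6 endoscopy, so an earlier withdrawal can rest only on symptoms or clinical judgement. That stands. A reader might infer that 4.4.1 lets the investigator withdraw subjects for the negative result of the primary outcome itself, but no section equates the two. Early failure is at most a correlate of non-response.

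A reader might also infer that a subject could be withdrawn once a failing week-6 biopsy is known. The documents do not support this. Section 4.4 concerns early withdrawal, and participation is complete after the 6-week endoscopy. A subject with that count has the primary outcome, so a failing result gives Section 6.3 no reason to exclude it.

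Nor is every withdrawal certain to be a non-responder or to raise the rate. Losing one responder from 15/20 gives 14/19 = 73.7%, which is lower.

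There are partial safeguards: the caution against unnecessary withdrawal, the optional end-of-study visit, the independent monitor's check that withdrawals are reported and explained (9.1), and a schedule with no visit between Day 1 and week 6. The last limits early judgements of failure but does not rule them out, because the symptom diary restarts two weeks before the final visit and adverse events are reviewed weekly or as needed (7.5). None of these returns a withdrawn subject to the denominator.

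Finally, 4.4.1 by itself excludes nobody from the analysis; 6.2 and 6.3 do. That is correct, and the remedy has to change both places. It is also fair that the shift with two withdrawals is small beside the width of the interval in a pilot of this size. But the interval describes sampling error and does not cover a bias that is expected to run in one direction.

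**Conclusion.** The concern holds in a limited form. Followed as written, the plan allows subjects judged to be failing to leave before the week-6 biopsy and drop out of the response rate. The expected effect is an upward bias. For a reported 75%, the rate with these subjects counted would be 75% with none withdrawn, 68.2% with two and 62.5% with four, assuming that all of them are true non-responders. The counts are illustrations, since the documents give no figure, and the bias shrinks or reverses if enough of the withdrawn would have responded. The documents show that the permission exists. They do not show that it was or will be used.

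**What to change.** **Section 4.4.1.** Separate stopping the diet from leaving the study. Treatment failure should not by itself be a ground for ending follow-up, and the week-6 outcome that is already scheduled should be sought with the subject's agreement. Whether the diet continues stays with the treating physician.

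**Sections 6.2 and 6.3.** State that a subject who started the diet and was withdrawn for treatment failure without a week-6 biopsy counts as a non-responder in the primary response rate. Report the completers-only rate as a sensitivity analysis, and list every withdrawal with its reason. Both parts are needed: with 4.4.1 alone changed, a subject who stays in the study but has no biopsy would still be excluded.

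**Cost.** A short amendment to these sections, with no visit beyond the existing schedule. The reported rate may be slightly less favourable. Counting those without a biopsy as non-responders is also a conservative convention that will misclassify any who would have responded, and the sensitivity analysis shows how much rests on it.

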4.4.2 Lost to Follow-Up

A subject will be considered lost to follow-up after documentation has been made of at least three documented attempts to contact (via phone or email). At that point a certified letter should be mailed to the subject's home address. If there is still no response after the certified letter is delivered, then the subject will be withdrawn from the study as lost to follow-up.

4.4.3 Data Collection and Follow-up for Withdrawn Subjects

Patients who withdraw prematurely from the study may be asked to complete an end of study visit per the study procedures. In addition, any ongoing adverse drug reactions or study-related adverse events will be followed until resolution or documentation of why there will be no resolution if the event will be ongoing.

5 Study Procedures

| Procedure | Screening Visit | Day 1 Visit | 6 Week Follow-Up Visit (+/- 7 days) |
|---|------------------|----------------|-------------------------------------|
| Eligibility Review | X | | |
| Informed Consent | X | | |
| Demographics | X | | |
| Medical History | X | | |
| Current Medications | X | X | |
| Vital Signs | X | | X |
| Questionnaires | X | | X |
| Research blood collection | X ¹ | | X |
| EGD with EREF and biopsies | X ^{1,2} | | X ² |
| Adverse Events | X | X | X |
| Dysphagia Symptom Questionnaire (DSQ) | | X ³ | X ³ |
| Nutrition Counseling | | X ² | |
| Allergy Skin Testing | | X ⁴ | |
| Diet Elimination | | X ⁵ | |

¹ Subjects must be scheduled for a routine care EGD with biopsies (clinical and research) at UNC or have had a routine care EGD with clinical and research biopsies at UNC within 3 months prior to enrollment. If subjects have had a recent EGD as defined above, then results from clinical biopsies taken during that EGD will be used to assess eligibility for this study, and research biopsies and EREFs from that EGD will also be used for this study. In these cases, an additional EGD does not need to be performed. In addition, if research blood was collected during the recent EGD and can be used in this study, then subjects will have an abbreviated blood collection during the screening visit. If subjects have not had an EGD with research and clinical biopsies at UNC within 3 months of enrollment, then they must be scheduled to receive a routine care EGD with biopsies at UNC during which clinical and research biopsies will be collected for this study.

² These procedures are considered routine care and are billed to the subject and/or subject's insurance.

³ The DSQ is started 2 weeks prior to the Day 1 and 6 week visits.

⁴ Results from the allergy skin testing will not be used to drive the food elimination diet.

⁵ Subjects will begin diet elimination on day 1 and continue for 6 weeks.

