5.2 Day 1 Visit

Two weeks prior to the day 1 visit, and while the lab performs T-cell and IgG4 signatures testing, subjects will be asked to fill out the Dysphagia Symptom Questionnaire (DSQ). The DSQ is a daily 3-question symptom diary to be completed nightly over a 2 week time period. This can be done on paper or by email.

During the day 1 visit, subjects will be scheduled for a routine care nutrition counseling appointment. During this appointment subjects will be advised how to effectively follow an elimination diet based on the specific triggers identified between Screening and Day 1 using samples obtained for the research study and will undergo allergy skin prick testing as a research procedure. Results from the allergy skin prick testing will not be used to drive the food elimination diet.

Subjects will be instructed to eliminate between 1 and 5 foods (dairy, wheat, egg, soy, and/or nuts) based on results from the T-cell and IgG4 signatures. Subjects will adhere to the elimination diet for 6 weeks

The following procedures will be completed during the day 1 visit

- DSQ (started 2 weeks prior to day 1 visit)
- Current medications
- Adverse events
- Nutrition counseling as per routine care
- Begin 6 week diet elimination therapy
- CRF completion

5.3 6 Week Follow-Up Visit (+/- 7 days)

Two weeks prior to the 6 week follow-up visit, subjects will be asked to fill out the Dysphagia Symptom Questionnaire (DSQ). The DSQ is a daily 3-question symptom diary to be completed nightly over a 2 week time period. This can be done on paper or by email.

After completion of the 6 week food elimination diet, subjects will return to one of the UNC endoscopy centers and undergo repeat EGD for routine care. During the EGD, clinical biopsies will be obtained. No research biopsies are collected for this study during the 6 week follow-up EGD. Follow up blood samples are collected. Subjects will complete the same questionnaires as the screening visit.

The following procedures will be completed during the 6 week follow-up visit

- DSQ (started 2 weeks prior to 6 week follow-up visit)
- Vital Signs
- Questionnaires
- EGD with EREF score and biopsies for pathology, per routine care (no research biopsies are obtained at the 6 week follow-up visit for this study)
- Blood collection
- Adverse events

Study participation is complete after completion of the 6 week follow-up visit.

6 Statistical Plan

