8.1 Confidentiality

Information about study subjects will be kept confidential and managed according to the requirements of the Health Insurance Portability and Accountability Act of 1996 (HIPAA). Those regulations require a signed subject authorization informing the subject of the following:

- What protected health information (PHI) will be collected from subjects in this study

- Who will have access to that information and why
- Who will use or disclose that information
- The rights of a research subject to revoke their authorization for use of their PHI.

In the event that a subject revokes authorization to collect or use PHI, the investigator, by regulation, retains the ability to use all information collected prior to the revocation of subject authorization. For subjects that have revoked authorization to collect or use PHI, attempts should be made to obtain permission to collect at least vital status (i.e. that the subject is alive) at the end of their scheduled study period.

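### The week-6 eosinophil count of withdrawn subjects is not a planned collection, though it comes from a routine-care EGD; excluding dropouts can bias the single-arm response rate upward

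*Combined protocol and SAP*

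**What the plan says.** **Outcome and its source.** The primary outcome in Section 3.4 is a "post-treatment esophageal eosinophil count of <15 eos/hpf". Section 3.1 gives the source: "At 6 weeks subjects will be scheduled for a routine care esophagogastroduodenoscopy (EGD) with biopsies for clinical purposes". Section 5.3 says that after the diet "subjects will return to one of the UNC endoscopy centers and undergo repeat EGD for routine care", and adds: "No research biopsies are collected for this study during the 6 week follow-up EGD". The Section 5 schedule sets the visit at 6 weeks +/- 7 days, and its footnote 2 classes the EGD as routine care.

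**After withdrawal.** Section 4.4.3 reads: "Patients who withdraw prematurely from the study may be asked to complete an end of study visit per the study procedures". It also requires that "any ongoing adverse drug reactions or study-related adverse events will be followed until resolution", or that a reason for non-resolution be documented. When a subject revokes authorization, Section 8.1 keeps the data already collected and says "attempts should be made to obtain permission to collect at least vital status".

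**Who may be withdrawn.** Section 4.4.1 lets the investigator withdraw a patient for, among other reasons, an adverse event, treatment failure or a protocol violation.

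**Analysis.** Sections 6.2 and 6.3 exclude patients who drop out or whose outcome data are incomplete. The reason in Section 6.2 is that "a subject must complete this end of treatment evaluation for us to be able to include their data in the analysis". It expects no selection bias because there are no arms to compare, and it describes dropout as low without giving a figure.

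**The concern.** A subject can leave the research part of this study and still produce the primary datum, at the same centre and with no research biopsy. The plan does not make use of this. Whether a withdrawn subject is asked back is discretionary. The content and timing of that visit are not tied to the week-6 window, and stopping the diet is not distinguished from leaving follow-up.

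The analysis rule adds to the problem. As worded, dropping out is enough for exclusion, whether or not a biopsy exists. Some of the permitted reasons for withdrawal are plausibly linked to non-response: treatment failure directly, protocol violation through poor adherence. In an open single-arm study the response proportion is itself the result, so losing non-responders raises it directly. The absence of a comparison arm gives no protection.

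What is at stake is the 75% response target and the rates that Section 6.1 intends to carry into the design of a randomized study.

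**Working it through.** **Inputs.** From Section 6.1: up to 30 enrolled, a goal of 20 completers, and 15 responders. From Sections 6.2 and 6.3: completers only are analysed. Assumed: m, the number of subjects who start the diet and then withdraw without an analysed outcome. The documents give no value for m.

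**The plan's own figures.** 15/20 = 75%, as stated. The printed 95% interval of 47-92% does not reproduce from 15/20; the exact (Clopper-Pearson) interval is 50.9-91.3%. This point does not depend on that interval.

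**Step 1: reported rate.** Withdrawn subjects enter neither numerator nor denominator, so the reported rate is 15/20 = 75% for every m.

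**Step 2: possible rate over all treated subjects.** The lower bound, with no withdrawn subject responding, is 15/(20 + m). The upper bound, with all responding, is (15 + m)/(20 + m).

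| m (assumed) | Lower bound | Upper bound |
|---|---|---|
| 2 | 15/22 = 68.2% | 17/22 = 77.3% |
| 4 | 15/24 = 62.5% | 19/24 = 79.2% |
| 6 | 15/26 = 57.7% | 21/26 = 80.8% |
| 8 | 15/28 = 53.6% | 23/28 = 82.1% |
| 10 | 15/30 = 50.0% | 25/30 = 83.3% |

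The last row is a ceiling. It treats the whole gap from 30 to 20 as withdrawal after the diet began. Consent and enrolment precede the qualifying EGD (Section 3.1), and subjects without confirmed active EoE or without research biopsies become screen fails, so some of those 10 would never be treated.

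**Step 3: direction.** If withdrawn subjects respond at rate r, the rate over all treated subjects is (15 + m x r)/(20 + m). With m = 4:

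- r = 0.25: 16/24 = 66.7%
- r = 0.50: 17/24 = 70.8%
- r = 0.75: 18/24 = 75.0%

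The completer rate is too high whenever r is below 75%, and unbiased only if the withdrawn respond as often as completers.

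**Step 4: what recovery gains.** The width of the bounds is m/(20 + m). With m = 4 this is 4/24 = 17 percentage points. If two of the four have an in-window routine EGD (also an assumption), 2/24 = 8 points remain.

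**Step 5: would a recovered biopsy count?** Section 6.3 excludes on either of two grounds, dropping out or incomplete data, so a dropout with a biopsy is still excluded. The reason in Section 6.2 makes completion of the end-of-treatment evaluation the condition, which such a subject arguably meets. The text does not settle the matter, and it could be decided after the result is known.

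**The case against.** The strongest case on the other side is that this is a small proof-of-principle study with dropout expected to be low, and that the 4.4.3 visit may already be the week-6 visit with its EGD. Nothing shows that someone who abandons the diet would still attend for an EGD. Subjects lost to follow-up cannot be asked, and participation stops on pregnancy. Section 3.4 also requires counts by the study's own validated method, which a routine pathology report may not use.

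Much of this stands as a limit on the gain. It does not remove the gap: a visit that may happen, at no stated time, is not a plan to obtain the week-6 count. As to the counting method, completers' week-6 counts also come from clinical biopsies, so the same reading can be applied to a withdrawn subject's slides.

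A reader might infer more than the documents support:

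- **That nothing else is followed after withdrawal.** Section 4.4.3 requires adverse-event follow-up. Vital status in Section 8.1 is a minimum, not a limit.
- **That permission to use the routine pathology is never sought.** The consent pages are not in the review copy, so this cannot be shown.
- **That withdrawn subjects would have an EGD in the first week or two of the diet.** No section places the visit at the time of withdrawal.
- **That a third of enrolled subjects are expected to drop out.** The margin from 20 to 30 may include screen fails.

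**Conclusion.** The point holds as a gap in planned outcome collection, made worse by the exclusion rule. Post-withdrawal collection of the primary outcome is left to discretion, the analysis set appears to drop such subjects even when a biopsy exists, and withdrawal can be related to response. With 15 of 20 completers responding, the reported 75% could stand for 68.2-77.3% of treated subjects with 2 withdrawals, or 62.5-79.2% with 4. The 50.0-83.3% range at 10 withdrawals is an outer limit, not an expectation.

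The upward direction rests on the withdrawn responding less often than completers. That is plausible given Section 4.4.1, but the documents do not establish it. With no withdrawals after Day 1 there is no effect. The documents do not show that bias will occur, only that the plan as written neither prevents it nor allows it to be measured.

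**What to change.** - **Section 4.4.3.** State that every subject who started the diet and then stops the diet or the research procedures will be asked for permission to collect the pathology, eosinophil count and EREF score from any routine-care EGD done at 6 weeks (+/- 7 days) after Day 1. Reconcile the content and timing of the end-of-study visit with the Section 5 schedule.
- **Section 8.1.** Keep vital status, and add this EGD result beside it as something for which permission may be sought after revocation.
- **Sections 6.2 and 6.3.** State that any subject who started the diet and has a biopsy in the window is included in the primary analysis, regardless of withdrawal or adherence. Both this and the 4.4.3 change are needed, since a collected result could otherwise still be excluded.

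**Cost.** Protocol wording, possibly consent and authorization wording, and a few chart reviews. No procedure is added. The Section 6 change also commits the primary estimate to subjects who started the diet rather than those who completed it, which should be stated openly. Some withdrawn subjects will have no EGD, so the number of outcomes recovered may be small.

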6.1 Sample Size Determination

Because this is a proof-of-principle effectiveness study without a comparison group, there is not a formal sample size calculation. However, we plan to consent and enroll up to 30 subjects with a goal of 20 subjects completing the study to show that 75% (15) have a histologic response to the allergen-specific immune-signature dietary elimination. We feel that this is a robust number of patients to demonstrate a preliminary effect, while also being a realistic number to enroll during this pilot study. In addition, while the 95% CIs around this goal are somewhat wide (47-92%), current allergy testing only has the ability to accurately predict triggers 13% of the time, so even if we are at the lower end of the range, it's still a major clinical step forward in practice.

In the proposed study, we will be performing the first prospective effectiveness study of an allergen-specific immune signature-based individualized dietary elimination regimen in patients with EoE. Because we are conducting what will essentially be a pilot or proof-of-principle study, the data we collect, including response rates and magnitude of response, will directly inform a planned large scale (ie R01) grant application for a randomized study of immune-signature-based elimination versus empiric food elimination.

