7.2 Recording of Adverse Events

At each contact with the subject, the investigator must seek information on adverse events by specific questioning and, as appropriate, by examination. Information on all adverse events should be recorded immediately in the source document, and also in the appropriate adverse event module of the case report form (CRF). All clearly related signs, symptoms, and abnormal diagnostic procedures results should be recorded in the source document, though should be grouped under one diagnosis.

All adverse events occurring during the study period must be recorded. The clinical course of each event should be followed until resolution, stabilization, or until it has been determined that the study treatment or participation is not the cause. Serious adverse events that are still ongoing at the end of the study period must be followed up to determine the final outcome. Any serious adverse event that occurs after the study period and is considered to be possibly related to the study treatment or study participation should be recorded and reported immediately.

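### Medications are not scheduled for review at week 6 and no analysis covers EoE-active drugs started or increased after the baseline EGD, so a drug response could be counted as a diet response

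*Combined protocol and SAP*

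**What the plan says.** **Collection.** The section 5 schedule has the row "Current Medications | X | X", with marks under Screening and Day 1 and none under week 6. Section 5.3 opens its list with "The following procedures will be completed during the 6 week follow-up visit". It then names the DSQ, vital signs, questionnaires, EGD with EREF score and biopsies, blood and adverse events, but not medications. Participation ends at that visit.

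**Eligibility.** The only drug criterion, in section 4.2, looks back from baseline: "Any corticosteroid exposure in the 4 weeks prior to their baseline endoscopic exam". Under section 3.1 that EGD may be up to 3 months before enrollment, and in some cases older samples may be used.

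**Outcome and analysis.** Section 3.4 defines the primary outcome as "histologic response, defined as a post-treatment esophageal eosinophil count of <15 eos/hpf". Section 6.2 says "the number of subjects with <15 eos/hpf on follow-up endoscopy will be calculated". Section 6.3 gives the only exclusion: "Patients who drop out or who have incomplete data for the outcomes will be excluded from analysis". None of these mentions concomitant drugs.

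**Purpose.** Section 6.1 sets a goal of 20 completers "to show that 75% (15) have a histologic response". It adds that the response rate will feed a grant application for a randomized study.

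**The concern.** The primary result is one proportion from one arm. No control group shares background drug use, so only the individual medication record could separate a response to the assigned diet from a response to a drug begun along the way. The protocol itself recognises such a drug: section 1.2 names topical corticosteroids as an alternative for patients who cannot keep to dietary therapy. The baseline biopsy is protected by a corticosteroid look-back. The follow-up biopsy, which decides the primary outcome, has no corresponding record or rule.

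Where a drug produced the response, the error runs one way: it raises the rate credited to the diet, and that rate is to inform the next trial. An analysis rule can be added later, but it cannot supply medication data that were never collected.

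**Working it through.** **1. Is the blank cell real?** The adverse events row of the same table is marked in all three columns, and vital signs, questionnaires, blood, EGD and DSQ are all marked at week 6. The blank is therefore not a fault across the whole table. The visit lists agree with it: medications appear in the lists for Screening (5.1) and Day 1 (5.2), but not in 5.3.

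**2. There are two gaps of different length.**
- *Collection gap:* Day 1 to the follow-up EGD. The visit is at 6 weeks +/- 7 days, so 42 - 7 = 35 days to 42 + 7 = 49 days. Drugs begun between the baseline EGD and Day 1 and still in use then fall under the Day 1 record.
- *Analysis gap:* the whole interval from baseline EGD to follow-up EGD. Even a drug recorded at Day 1 has no stated consequence in 6.2 or 6.3.

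**3. The plan's own figures.** The goal count reproduces: 0.75 x 20 = 15. The interval of 47-92% in section 6.1 does not reproduce for 15/20. The exact (Clopper-Pearson) 95% interval is 50.9-91.3%, and the Wilson, Agresti-Coull, Jeffreys and Wald intervals do not give 47-92% either. The present point does not depend on that figure, and exact intervals are used below.

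**4. Weight of one subject.** 1/20 = 5 percentage points.

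**5. Worst-case reclassification.** Let k be the number of the 15 responders who were exposed, and suppose that every one of them would have failed on diet alone. The documents give no value for k, so 0 to 3 is an assumed range. With x = 15 - k and n = 20, the exact limits are the 0.025 quantile of Beta(x, n - x + 1) and the 0.975 quantile of Beta(x + 1, n - x).

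| k | Responders | Rate | Exact 95% CI |
|---|---|---|---|
| 0 | 15/20 | 75% | 50.9-91.3 |
| 1 | 14/20 | 70% | 45.7-88.1 |
| 2 | 13/20 | 65% | 40.8-84.6 |
| 3 | 12/20 | 60% | 36.1-80.9 |

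These are maximum shifts for each k. An exposed responder who would have responded to diet anyway contributes no error.

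**The case against.** **Other routes may reveal drug use.** Section 7.2 says that at each contact "the investigator must seek information on adverse events by specific questioning", and section 7.1 treats worsening of a preexisting condition as an adverse event. Section 8.2 lists clinic and hospital charts as source documents. Section 4.4.1 lets the investigator withdraw a subject for treatment failure or protocol violation, and treatment failure is close to the scenario at issue. This stands in part, because these routes may catch some cases. None requires medications to be collected or says how an exposed responder is counted. Withdrawal is discretionary, no on-study drug use is defined as a violation, and the same section discourages unnecessary withdrawals.

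**The visit lists are not exhaustive.** The Day 1 list omits the skin test that the schedule and the Day 1 text require, and the week-6 list omits CRF completion. The CRF and the content of the week-6 questionnaires are not described. Absence from 5.3 is therefore only supporting evidence, and the schedule cell carries most of the weight.

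**Counting the outcome whatever drugs were taken is a defensible choice.** The objective is effectiveness, in a pilot with no comparator, no formal sample size and no interim decision. This stands, and it is why the stated rate should remain primary. It does not justify leaving the exposure unrecorded.

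**The size is small against the noise.** Five points compares with an exact interval about 40 points wide (91.3 - 50.9 = 40.4). That is fair, although section 2 hypothesises a response of at least 75%, and a single reclassification takes 15/20 below it.

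**Conclusion.** The point holds as a gap in collection and analysis. As written, the plan cannot reliably detect a drug response or separate it from a diet response. At 20 completers the effect is at most 5 points per exposed responder, and the number exposed is unknown.

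A reader might infer more than the documents support:
- *That the response rate will be inflated.* Nothing states or implies how often such drugs would be started, so the bias is possible, not shown.
- *That no medication data exist after the baseline EGD.* Day 1 has a medication record. Only Day 1 to week 6 lacks one.
- *That a likely size can be given.* Any expected shift needs a diet response rate, a drug response rate and a link between exposure and diet response. The simplest assumption, that exposure is unrelated to diet response, conflicts with section 1.2, where the drug is an alternative for patients who cannot follow the diet. No expected effect follows from the documents.
- *That the primary rate and a reclassified rate bracket the diet-only rate.* This would also need complete ascertainment, no drug effect that prevents response, and no carry-over from non-steroid drugs begun shortly before baseline. None of these is assured.

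This is a worthwhile, low-cost improvement and not a flaw that invalidates the study.

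**What to change.** 1. Add current medications, including changes since the baseline EGD, to the week-6 column of the section 5 schedule and to the list in 5.3.
2. In 6.2, keep the stated response rate as primary and add: *Subjects who newly started or increased a corticosteroid or other EoE-active treatment between the baseline and follow-up EGDs will be listed, using a list of treatments fixed before the first subject's follow-up biopsy is read. As a sensitivity analysis, the response rate with exact 95% CI will also be reported with such responders counted as non-responders.*
3. Present the second rate as a conservative sensitivity result, not as a bound.

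The treatment list must precede the first reading because follow-up biopsies are routine clinical ones and may be read subject by subject.

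**Cost.** An existing item is repeated at an existing visit, with change dates that may reach back more than 3 months where an older baseline EGD is used. One listing and one extra rate are added. The sensitivity rate may be lower than the primary rate and may understate the diet effect, since some exposed responders would have responded anyway. No clinical rule on drug use is proposed.
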